8.2. Safety Assessments

Safety is the primary objective of the study.

The primary endpoint of the study is to assess treatment-emergent adverse events (TEAE) in children with AOM receiving Augmentin (ES)-600 at a dose of 90/6.4 mg/kg/day in two divided doses, administered for 10 days.

Incidence of PDD will be evaluated as secondary endpoint, along with efficacy parameters. protocol-defined diarrhea (PDD) is defined as:

- 3 or more watery stools in one day OR
- 4 or more loose/watery stools in one day OR
- 2 watery stools per day for two consecutive days OR
- 3 loose/watery stools per day for two consecutive days.

Participants who withdraw due to diarrhea or has a documented SAE of diarrhea will be considered to have fulfilled the criteria for PDD and will be analyzed as such, even in the absence of Patient Diary card data.

8.2.1. Physical Examinations

- Physical examination will include, at a minimum, assessments of the skin, cardiovascular, respiratory, gastrointestinal, and neurological systems. Height and weight will also be measured and recorded.
- Investigators should pay special attention to clinical signs related to previous serious illnesses.

8.2.2. Vital Signs

- Body temperature, pulse rate, and respiratory rate will be assessed.
- Pulse measurements will be assessed with a completely automated device. Manual techniques will be used only if an automated device is not available.
- Pulse measurements should be preceded by at least 5 minutes of rest for the participant in a quiet setting without distractions.

8.2.3. Clinical Safety Laboratory Assessments

Refer to [Appendix 2](#) for the list of clinical laboratory tests to be performed and to the SoA for the timing and frequency. The evaluations will be performed at local laboratory at each site.

All protocol-required laboratory assessments, as defined in [Appendix 2](#), must be conducted in accordance with the SoA.

8.2.4. Radiographic Evaluations (X Ray)

An X ray will be performed only at preliminary visit at the study site. Chest X ray and X ray of nasal/paranasal sinus to be performed for patients presumed to have CABP and ABRS. The X ray is not mandatory and performed only for reference, as per investigators discretion. The purpose of radiographic evaluation is only to confirm the diagnosis when CABP or ABRS clinically, reasonably suspected but can't be confirmed with clinical criteria. Since children demonstrates signs and symptoms of CABP differently than adults and may deteriorate more rapidly than adults, keeping an option of chest X ray in the inclusion criteria is critical for investigators to rule out any need for hospitalization.

8.3. Adverse Events and Serious Adverse Events

The definitions of an AE or SAE can be found in [Appendix 3](#).

The definitions of device-related safety events, (adverse device effects [ADEs]) and serious adverse device effects (SADEs), can be found in [Appendix 5](#). Device deficiencies are covered in Section [8.3.9](#).

AEs will be reported by the participant (or, when appropriate, by a caregiver, surrogate, or the participant's legally authorized representative).

The Investigator and any qualified designees are responsible for detecting, documenting, and reporting events that meet the definition of an AE or SAE and remain responsible for following up AEs that are serious, considered related to the study intervention or the study, or that caused the participant to discontinue the study intervention or study (see Section [7](#)).

8.3.1. Time Period and Frequency for Collecting AE and SAE Information

- All SAEs will be collected from the signing of the informed consent form until the follow-up visit at the time points specified in the SoA (Section [1.3](#)).
- All AEs will be collected from the start of study intervention until the follow-up visit at the time points specified in the SoA (Section [1.3](#)).

- Medical occurrences that begin before the start of study intervention but after obtaining informed consent will be recorded on the Medical History/Current Medical Conditions section of the case report form (eCRF) not the AE section.
- All SAEs will be recorded and reported to the Sponsor or designee immediately and under no circumstance should this exceed 24 hours, as indicated in [Appendix 3](#). The Investigator will submit any updated SAE data to the Sponsor within 24 hours of it being available.
- Investigators are not obligated to actively seek AEs or SAEs after the conclusion of the study participation. However, if the Investigator learns of any SAE, including a death, at any time after a participant has been discharged from the study, and he/she considers the event to be reasonably related to the study intervention or study participation, the Investigator must promptly notify the Sponsor.

8.3.2. Method of Detecting AEs and SAEs

- The method of recording, evaluating, and assessing causality of AEs and SAEs and the procedures for completing and transmitting SAE reports are provided in [Appendix 3](#).
- Care will be taken not to introduce bias when detecting AE and/or SAE. Open-ended and non-leading verbal questioning of the participant is the preferred method to inquire about AE occurrence.
- Physical examination may reveal certain AEs not reported by the participant.

8.3.3. Follow-up of AEs and SAEs

After the initial AE/SAE report, the Investigator is required to proactively follow each participant at subsequent visits/contacts. All SAEs, will be followed until the event is resolved, stabilized, otherwise explained, or the participant is lost to follow-up (as defined in Section [7.3](#)). Further information on follow-up procedures is given in [Appendix 3](#).

8.3.4. Regulatory Reporting Requirements for SAEs

- Prompt notification by the Investigator to the Sponsor of a SAE is essential so that legal obligations and ethical responsibilities toward the safety of participants and the safety of a study intervention under clinical investigation are met.
- The Sponsor has a legal responsibility to notify both the local regulatory authority and other regulatory agencies (if applicable) about the safety of a study intervention under clinical investigation. The Sponsor will comply with country-

specific regulatory requirements relating to safety reporting to the regulatory authority, Institutional Review Boards (IRB)/Independent Ethics Committees (IEC), and Investigators.

- For all studies except those utilizing medical devices Investigator safety reports must be prepared for suspected unexpected serious adverse reactions (SUSAR) according to local regulatory requirements and Sponsor policy and forwarded to Investigators as necessary.
- An Investigator who receives an Investigator safety report describing a SAE or other specific safety information (eg, summary or listing of SAEs) from the Sponsor will review and then file it and will notify the IRB/IEC, if appropriate according to local requirements.

8.3.5. Pregnancy

- Details of all pregnancies in female participants will be collected at Day 0.
- Participants will be instructed to notify the Investigator if they become pregnant during study period. Such participants will be immediately withdrawn from the study.
- Any reported pregnancy must be informed to Sponsor by Investigator within 24 hours of receipt of information and should follow the procedures outlined in [Appendix 4](#).
- Any abnormal pregnancy outcomes (eg, spontaneous abortion, fetal death, stillbirth, congenital anomalies, ectopic pregnancy) are considered SAE.

8.3.6. Cardiovascular and Death Events

For any cardiovascular events detailed in [Appendix 3](#) and all deaths, whether they are considered SAEs, specific Cardiovascular (CV) and Death sections of the eCRF will be required to be completed. These sections include questions regarding cardiovascular (including sudden cardiac death) and non-cardiovascular death.

The CV eCRFs are presented as queries in response to reporting of certain CV MedDRA terms. The CV information should be recorded in the specific cardiovascular section of the eCRF within one week of receipt of a CV event data query prompting its completion.

The Death eCRF is provided immediately after the occurrence or outcome of death is reported. Initial and follow-up reports regarding death must be completed within 1 week of when the death is reported.

8.3.7. Disease-Related Events and/or Disease-Related Outcomes Not Qualifying as SAEs

There are no disease related events (DREs) commonly seen in participants with AOM which can be serious/life-threatening.

8.3.8. Adverse Events of Special Interest

There are no adverse events of special interest planned to be monitored.

8.3.9. Medical Device Deficiencies

Medical devices are being provided for use in this study to measure and administer the study intervention. In order to fulfil regulatory reporting obligations worldwide, the Investigator is responsible for the detection and documentation of events meeting the definitions of device deficiency that occur during the study with such devices.

The definition of a Medical Device Deficiency can be found in [Appendix 5](#).

NOTE: Incidents fulfilling the definition of an AE/SAE will also follow the processes outlined in Section [8.3.3](#) and [Appendix 3](#) of the protocol.

8.3.9.1. Time Period for Detecting Medical Device Deficiencies

- Medical device deficiencies will be detected, documented, and reported during all periods of the study in which the medical device is used.
- If the Investigator learns of any device deficiency at any time after a participant has been discharged from the study, and such device deficiency is considered reasonably related to a medical device provided for the study, the Investigator will promptly notify the Sponsor.

The method of documenting Medical Device Incidents is provided in [Appendix 5](#).

8.3.9.2. Follow-up of Medical Device Deficiencies

- Follow-up applies to all participants, including those who discontinue study intervention or the study.
- The Investigator is responsible for ensuring that follow-up includes any supplemental investigations as indicated to elucidate the nature and/or causality of the deficiency.
- New or updated information will be recorded on the originally completed form with all changes signed and dated by the Investigator.

8.3.9.3. Prompt Reporting of Medical Device Deficiencies to Sponsor

- Device deficiencies will be reported to the Sponsor within 24 hours after the Investigator determines that the event meets the protocol definition of a device deficiency.
- The Medical Device Deficiency Report Form will be sent to the Sponsor by fax. If fax is unavailable, then email should be utilized.
- The Sponsor will be the contact for the receipt of device deficiency reports.

8.3.9.4. Regulatory Reporting Requirements for Medical Device Incidents

- The Investigator will promptly report all deficiencies occurring with any medical device provided for use in the study for the Sponsor to fulfill the legal responsibility to notify appropriate regulatory authorities and other entities about certain safety information relating to medical devices being used in clinical studies.

The Investigator, or responsible person according to local requirements (eg, the head of the medical institution), will comply with the applicable local regulatory requirements relating to the reporting of device deficiencies to the IRB/IEC.

8.4. Treatment of Overdose

For this study, any dose of Augmentin (ES)-600 greater than 90/6.4 mg/kg/day within a 24-hour time period will be considered an overdose.

Sponsor does not recommend any specific treatment for an overdose.

In the event of an overdose, the Investigator should:

5. Contact the Medical Monitor immediately.
6. Document the quantity of the excess dose as well as the duration of the overdosing in the eCRF.

Further decision regarding dose interruptions or modifications will be made by the Investigator in consultation with the Medical Monitor based on the clinical evaluation of the participant.

8.5. Pharmacokinetics

Pharmacokinetic parameters are not evaluated in this study.

8.6. Pharmacodynamics

Pharmacodynamic parameters are not evaluated in this study.

8.7. Genetics

Genetics are not evaluated in this study.

8.8. Biomarkers

Biomarkers are not evaluated in this study.

8.9. Immunogenicity Assessments

Immunogenicity assessments are not evaluated in this study.

8.10. Health Economics OR Medical Resource Utilization and Health Economics.

Health Economics/Medical Resource Utilization and Health Economics parameters are not evaluated in this study.

9. STATISTICAL CONSIDERATIONS

9.1. Statistical Hypotheses

No formal hypothesis is considered.

9.2. Sample Size Determination

A total of 310 subjects will be enrolled and dosed. These 310 participants will be enrolled for each indication based on the respective prevalence as mentioned in [Table 7](#) below. These prevalence values are based on all ARTIs in India.

Table 7 Prevalence for Division of Sample Size

Study	Indication	Prevalence %
Kumari et al (2016)	AOM	17.6
Acharya et al (2003)	CAP	8.6 (0.5% severe)
Shahid et al (2012)	ABRS	14

The approximate ratio of samples in each indication will be 18:9:14 (AOM: CABP: ABRS). Based on this ratio, at least 136 subjects with AOM, 68 with CABP and 106 with ABRS will be enrolled for the study.

If the proportion of participants reporting at least one TEAE is 37.9% (as observed in [Young et al, 2003](#)), and assuming a sample size of 310 participants, it is estimated that the width of the 95% confidence interval would be within +/- 5.43% of the sample

proportion (ie, [32.5%, 43.3%]), which equates to the lower and upper bounds of the 95% confidence interval lying within approximately 14% of the estimated proportion.

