9.4.2. Primary Endpoint(s)

Statistical analyses on safety endpoints will be conducted using participants from the Intent-to-Treat (ITT) population.

Adverse Events

The primary safety endpoint is the incidence of participants reporting at least one TEAE combined across all the indications.

The primary estimand is the percentage of participants reporting at least one TEAE regardless of withdrawal from the study resulting in loss to follow-up. The while-on-treatment strategy will be used, which will count and analyse adverse event occurred during treatment effect (During treatment Period + lag time of 1day).

Apart from the TEAE, overall adverse events would be reported as collected (Treatment Policy).

The primary safety endpoint will be summarized using number and percentage of participants reporting any TEAEs and participants with at least one TEAE with corresponding exact 95% CI.

Participant incidence of all TEAEs will be tabulated by system organ class (SOC) and preferred term (PT). The number and percentage of participants reporting adverse events will be evaluated and will also be tabulated by relationship to study drug.

All summaries will be reported as overall summaries and also stratified by indication.

Further details will be provided in the Statistical Analysis Plan (SAP).

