## 6.7. STATISTICAL TESTS

The default significant level will be 5%. All confidence intervals will be computed at 95% and all tests will be two-sided, unless otherwise specified in the description of the analyses.

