## 6.8. SAMPLE SIZE ESTIMATION

A total of 310 subjects will be enrolled and dosed. These 310 participants will be enrolled for each indication based on the respective prevalence as mentioned in the table below.

These prevalence values are based on all ARTIs in India.

Study	Indication	Prevalence %
Kumari et al (2016)	AOM	17.6
Acharya et al (2003)	CAP	8.6 (0.5% severe)
Shahid et al (2012)	ABRS	14

The approximate ratio of samples in each indication will be 18:9:14 (AOM: CAP:ABRS). Based on this ratio, at least 136 subjects with AOM, 68 with CAP and 106 with ABRS will be enrolled for the study.

If the proportion of participants reporting at least one TEAE is 37.9% (as observed in Young et al, 2003), and assuming a sample size of 310 participants, it is estimated that the width of the 95% confidence interval would be within +/- 5.43% of the sample proportion (ie, [32.5%, 43.3%]), which equates to the lower and upper bounds of the 95% confidence interval lying within approximately 14% of the estimated proportion.

The sensitivity of the precision is calculated with respect to 5 different proportions estimated as presented below:

Proportion estimate	Sample size	Precision	95% CI
30%	310	5.10%	(24.9%, 35.1%)
35%	310	5.31%	(29.7%, 40.3%)
37.9%	310	5.43%	(32.5%, 43.3%)

40%	310	5.45%	(34.5%, 45.5%)
45%	310	5.54%	(39.5%, 50.5%)
50%	310	5.57%	(44.4%, 55.6%)

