#### 16.1.1. TEAES: PRIMARY SAFETY ENDPOINT

AEs occurring from when a subject sign informed consent to when a subject exits the study will be accounted for in the reporting. AEs occurring pre-treatment, treatment emergent adverse event (on-treatment) and post-treatment periods will be summarized and listed for the ITT population. A treatment -emergent adverse event is defined as any adverse event that develops after initiation of the study treatments or any adverse event already present that worsens following exposure to study treatment.

The primary safety endpoint will be summarized with counts and percentage of subjects reporting any TEAEs and subjects with at least one or any TEAE with corresponding 95% CI using exact binomial method

The following summaries will be generated for adverse events:

- Adverse event overview by period
- Adverse event overview by period for acute otitis media (AOM)
- Adverse event overview by period for acute bacterial rhinosinusitis (ABRS)
- Adverse event overview by period for community acquired bacterial pneumonia (CABP)
- Treatment emergent adverse events by system organ class, preferred term, overall and indication
- Adverse events by system organ class, preferred term, overall and indication - post-treatment
- Common ( $\geq 1\%$ ) treatment emergent adverse events by preferred term, overall and indication
- Common ( $\geq 1\%$ ) adverse events by preferred term, overall and indication - post-treatment

AEs and TEAEs will be sorted by descending order of system organ class (SOC) and total frequency of preferred term (PT) within each system organ class (SOC).

AEs and TEAEs related to study drug will be presented in decreasing order of preferred term (PT). Subjects listing of adverse events by indication (TEAE and post-treatment period) will be produced.

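### Minor correction: the ±5.43-point precision stated for the primary endpoint does not fit the formula behind the rest of Table 8, and is not the precision of the exact interval planned

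*Protocol*

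**What the plan says.** Protocol section 9.1 states that there is no formal hypothesis. The statistical support for 310 children is therefore the expected precision of the primary proportion, given in protocol sections 9.2 and 9.2.1 (Table 8) and repeated in SAP section 6.8.

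- Planning inputs, protocol 9.2: "If the proportion of participants reporting at least one TEAE is 37.9" per cent, and "assuming a sample size of 310 participants".
- Stated precision, protocol 9.2: "the width of the 95% confidence interval would be within +/- 5.43% of the sample". The same sentence prints limits of 32.5% and 43.3% and puts both at roughly 14% from the estimate in relative terms.
- SAP 6.8 has the same sentence: "it is estimated that the width of the 95% confidence interval would be within +/- 5.43% of the sample".
- Table 8, repeated in SAP 6.8, gives 5.10, 5.31, 5.43, 5.45, 5.54 and 5.57 points at 30, 35, 37.9, 40, 45 and 50%, all with 310 children. No formula is named.

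The planned analysis of the endpoint is exact in both documents. Protocol 9.4.2 will report "participants with at least one TEAE with corresponding exact 95% CI", and SAP 16.1.1 will report "subjects with at least one or any TEAE with corresponding 95% CI using exact binomial method". On level and sidedness, SAP 6.7 says: "All confidence intervals will be computed at 95% and all tests will be two-sided".

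**The concern.** The precision statement is the only quantitative argument for the sample size, so a reader should be able to reproduce it and it should describe the interval that will be reported. Neither holds fully. The base-case row, which is the one carried into the text, departs from the formula that fits its five neighbours. All six rows also appear to be symmetric normal-approximation half-widths, whereas the exact binomial interval is somewhat wider and, away from 50%, longer on the upper side. For an adverse event rate, the upper limit is the one that readers look at first.

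What is at stake is the accuracy of a stated property of the design. The choice of 310 and the validity of the analysis are not in question.

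**Working it through.** **Inputs.** p = 0.379 and n = 310 (protocol 9.2); 95% two-sided (SAP 6.7); exact binomial interval (protocol 9.4.2, SAP 16.1.1).

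**Step 1: the stated figure by the normal approximation.** Half-width = 1.96 × √(p(1−p)/n) = 1.96 × √(0.379 × 0.621 / 310) = 0.0540, or 5.40 points. The interval is 37.9 ± 5.40 = 32.5% to 43.3%. Using 5.43 instead gives 32.47% to 43.33%, which rounds to the same limits. Relative to the estimate, 5.40/37.9 = 14.2% and 5.43/37.9 = 14.3%. So the printed interval and the 14% statement hold under this formula. Only the 5.43 does not match.

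**Step 2: where 5.43 could come from.** Solving the same formula for n gives 1.96² × 0.379 × 0.621 / 0.0543² ≈ 306.6. At n = 310 it returns 5.43 if p is 39%. A t quantile with n−1 in the standard error gives 5.43 at 37.9%, but for 30, 35, 40, 45 and 50% that variant gives 5.13, 5.34, 5.48, 5.57 and 5.60, which matches none of the stated rows. The documents do not allow a choice among these origins.

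**Step 3: the exact interval.** The Clopper-Pearson limits, with x = np, are the 2.5% quantile of Beta(x, n−x+1) and the 97.5% quantile of Beta(x+1, n−x). All rows use n = 310.

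| Rate | Stated half-width | Wald | Exact half-width | Exact limits | Lower arm / upper arm |
|---|---|---|---|---|---|
| 30% | 5.10 | 5.10 | 5.24 | 24.95% to 35.44% | 5.05 / 5.44 |
| 35% | 5.31 | 5.31 | 5.45 | 29.70% to 40.59% | 5.30 / 5.59 |
| 37.9% | 5.43 | 5.40 | 5.54 | 32.48% to 43.56% | 5.42 / 5.66 |
| 40% | 5.45 | 5.45 | 5.59 | 34.50% to 45.69% | 5.50 / 5.69 |
| 45% | 5.54 | 5.54 | 5.68 | 39.37% to 50.72% | 5.63 / 5.72 |
| 50% | 5.57 | 5.57 | 5.70 | 44.30% to 55.70% | 5.70 / 5.70 |

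The exact half-width exceeds the stated one by 0.11 to 0.14 points in every row. At 37.9% the upper arm exceeds 5.43 by 5.66 − 5.43 = 0.23 points and is 5.66/37.9 = 14.9% of the estimate.

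**Step 4: whole counts.** 37.9% of 310 is 117.49 children, so the 37.9% row is a planning value that cannot be observed. The neighbouring counts agree with it: 117/310 gives 32.3% to 43.4% (half-width 5.54, upper arm 5.65) and 118/310 gives 32.6% to 43.7% (half-width 5.54, upper arm 5.66).

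**The case against.** The case for leaving the text alone has real weight.

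- The wording is an estimate and says within; a Wald half-width of 5.40 does lie within 5.43. The printed interval and the 14% statement are right under that formula.
- That Wald was the formula used is an inference from five matching rows. A slightly different formula or a rounded input could have produced 5.43.
- Planning with a normal approximation and analysing with an exact interval is common practice, and Table 8 does not claim to be exact.
- Under the exact method the lower limit at 37.9% is still 32.5% and the lower arm (5.42) still meets 5.43. At 30% and 35% the exact lower arms are shorter than the stated half-widths. The visible change in the base case is an upper limit of 43.6% in place of 43.3%.
- The exact half-width of 5.54 lies inside the 5.10 to 5.57 range that Table 8 already discloses, though the upper arm of 5.66 is just outside it.
- The reported interval will be exact in any case, so no reader of the results is misled.

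All of this stands, and it keeps the point minor. It does not remove it. Whatever produced 5.43, one row of a single column follows a different calculation from the other five, and the specified exact analysis does not give the stated upper limit at the planning rate.

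A reader might go further and infer that the study's precision is wrong, that the calculation was really made for 307 children, or that 310 is too few because the exact half-width reaches 5.43 only at about 323 children and the upper arm only at about 336. The documents support none of these. They describe the precision expected with 310, set no required half-width, and do not derive 310 from 5.43.

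**Conclusion.** The point holds as a minor correction. At 37.9% and n = 310, the stated 5.43 is 0.03 points away from the formula that reproduces the rest of Table 8. It is also 0.11 points narrower in half-width, and 0.23 points shorter on the upper side, than the exact interval specified for the primary analysis. Across the table the total width is understated by a similarly small amount; it would be too much to say that every bound is too narrow. The sample size, the analysis and the conclusions are unaffected.

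This rests on two assumptions: that the exact interval is Clopper-Pearson, the standard meaning of the term, and that all 310 children are dosed and so enter the ITT population, as the plan intends. That the table used the normal approximation is inferred and is not stated in the documents.

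**What to change.** Amend protocol sections 9.2 and 9.2.1 (Table 8) and SAP section 6.8 in one of two ways.

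1. Preferred: restate the precision for the planned exact interval. At 37.9% this is about 32.5% to 43.6%, half-width 5.5 points, upper arm 5.7 points, upper bound within about 15% of the estimate. Replace the Table 8 half-widths with 5.24, 5.45, 5.54, 5.59, 5.68 and 5.70, with the matching limits.
2. Alternatively, keep the normal approximation, name it as a planning approximation, change 5.43 to 5.40, and add the exact half-width beside each row.

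The cost is a few numbers and one sentence in each document. The stated precision becomes slightly less favourable under the first option, and nothing in the conduct or analysis of the study changes.
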